### ***Pilot measures***

Although dichotomous outcomes are unlikely to have enough variability in the present pilot studies, we will work to establish procedures to reliably collect this information within the current participants, in anticipation of collecting these data in a larger, future, clinical trial.

*Referral for special education.* All referrals from kindergarten and first grade for special education placement will be documented by the participating schools.

*Stimulant medication use.* Parents will be asked about the use of stimulant medication at any time during the school year.

*Grade retention.* At the end of each year, each participating child will be coded as being promoted or retained. This outcome will be assessed at the end of the kindergarten and 1st grade.

### ***Assessment of Hypothesized Mechanisms of Treatment Effect***

*Positive Student-Teacher Interactions.* The ratio of positive to negative statements issued by the teacher on the SBTR observational measure will be used as an indicator of student-teacher interactions, with

classrooms that have a positive environment having a larger number (i.e., more positives than negatives) relative to those that have a negative environment (i.e., fewer positives than negatives). Prior studies have demonstrated this information can be reliably collected (Vujnovic, et al., 2014). Further, these rates of positive to negative statements can be reliably modified based on background behavioral interventions such as the DRC (Fabiano et al., 2007). This measure will be collected across the three groups.

*Executive Functioning.* EF is thought to be a key construct in young children (e.g., Diamond & Lee, 2011). Despite the promise of studying EF in early development, researchers seeking to assess EF in early childhood face a number of conceptual and methodological problems (see, e.g., Best & Miller, 2010; Garon et al., 2008). Although numerous tasks have been employed to measure EF in early childhood (e.g., Carlson, 2005), many exhibit either ceiling or floor effects in the age range of the proposed study, use pass/fail rules that make them relatively insensitive, have too few items to reliably assess the construct of interest, and/or are conceptually “dirty”, making it difficult to know what process is being assessed (see, e.g., Best & Miller, 2010; Carlson, 2005; Garon et al., 2008; Willoughby et al., 2012). The proposed assessments are based in theory and empirical work that suggests that the great diversity of putative EFs likely build on three core functions: working memory, inhibitory control, and cognitive flexibility or set shifting (e.g., Garon et al., 2008; Miyake et al., 2000). *Working memory* is the capacity to maintain temporary, active representations of information and to manipulate that information, a function critical for planning, problem-solving, and decision-making (e.g., Baddeley 2003). *Inhibitory control* is itself multidimensional (e.g., Nigg, 2000), but here we focus on response inhibition, the ability to stop a typical or pre-potent response; in practical terms, this is the ability critical for refraining from ‘blurted out’ an answer to a teacher’s question. *Set shifting* involves flexibility of attention and responses when the rules/contingencies change. Set shifting likely involves both working memory and inhibition, but differs in its focus on adapting to changing circumstances (e.g., Best & Miller, 2010).

We seek to assess each of the three core domains in a relatively pure manner with developmentally sensitive and appropriate computerized tasks. Importantly, the proposed tasks are sensitive to cross-sectional age differences in the developmental period studied here; the proposed within-subjects approach will provide even greater power to detect developmental changes (e.g., Best & Miller, 2010; Carlson, 2005; Tillman et al., 2008). Ideally, we would assess each construct with multiple measures (e.g., Campbell & Fiske, 1959), but the additional time required to do so could seriously threaten construct validity within this young sample. Although we assess each domain separately, we will also consider constructing a single task-EF composite, given evidence that EF may be unidimensional in this age range and that such composites may exhibit better criterion validity than each separate index (e.g., Willoughby et al., 2012). We have had great success in collecting complete data from young children, including those with ADHD and other behavior problems, in more lengthy protocols for several consecutive days (e.g., Ashare, Hawk, et al., 2010; Bubnik et al., 2015; Hawk et al., 2018; Shiels, Hawk, et al., 2009; Spencer, Hawk, et al., 2009; Strand, Hawk et al., 2012). Task order is counterbalanced across participants.

All EF measures will be assessed at all four time points. This frame allows the maximal reasonable timeframe for assessment within the Kindergarten year (avoiding transition months of September and June). The Working Memory and Inhibitory Control tasks described below have mediated stimulant medication effects in an analogue elementary school classroom (Hawk et al., 2018; Preliminary Study 3), making them viable candidates as mechanisms for change in our RAE-focused intervention.

*Working Memory.* The spatial span task is a computerized adaptation (see Shiels, Hawk, et al., 2008) of prior working memory tasks, the Corsi blocks, and the WISC-IV spatial span measure (Kaplan et al, 2004; Luciana, 2003; Milner, 1971). An array of ten squares is presented on the computer screen. On each trial, a ☺ appears in a sequence of 2-8 squares (1/sec). For forward span, participants use a mouse to click the squares in the same order. For backward span, which requires manipulation of information in WM, participants click the squares in the reverse order. In each version, the task begins with a practice followed by 2-location sequences. The task ends when both trials within a difficulty level are incorrect. The number of trials correct is the primary dependent measure, with trials forward representing WM storage and trials backwards providing an index of WM manipulation (see Shiels, Hawk, et al., 2008).

*Inhibitory Control.* Response inhibition will be assessed using the stop task. The stop-signal paradigm (Logan, 1994; Logan et al., 1984) offers the most pure measure of response inhibition (e.g., Nigg, 2001). Participants button press to indicate whether the “go” signal (← or →) is pointing left or right, but are asked to not respond on trials when the stop signal (a brief tone or a second visual stimulus) is presented (25% of trials after the go stimulus). The stop signal delay adjusts dynamically based on whether the previous stop trial led to successful inhibition (next stop delay is longer, making it harder to inhibit) or a failure to inhibit (next stop delay

is shorter, making it easier to inhibit; Logan et al., 1997). The primary dependent variable, stop signal reaction time or SSRT, is an estimate of the speed of inhibitory processing.

*Set shifting.* To assess sensitivity and flexibility to changing task requirements and rules, we will employ the dimensional change card sort (DCCS) of Frye et al. (1995). To avoid ceiling effects on performance, we will follow the standard DCCS, followed by the advanced Borders DCCS (Carlson, 2005; Hongwanishkul et al., 2005) using the published protocol of Zelazo (2006). After brief initial practice, the child sorts stimuli that vary by shape (rabbit, boat) and color (red, blue). First, stimuli are sorted based on one dimension. Next, the rule switches to the other dimension. Most children in the present sample are expected to perform quite well on the first two stages. The advanced Borders DCCS is the last phase. In the borders version, children sort based on one dimension (color) if the stimulus has a black border around it, but based on the other dimension is there is no border. The Borders version will be scored continuously with the number sorted correctly serving as the primary dependent variable. Total testing time for the DCCS is 10 minutes.

### **Measures of Integrity and Fidelity**

To record the integrity and fidelity (Cordray & Pion, 2006; Gresham, 1989; Lane, Beebe-Frankenberger, Lambros, & Pierson, 2001; Waltz, Addis, Koerner, & Jacobson, 1993) with which the intervention is implemented, multiple procedures will be used.

Because date of birth is the primary independent variable in this study, we will verify each child's date of birth using the official Certificate of Live Birth required for kindergarten registration. This review will occur during the explanation of the informed consent document that is conducted at kindergarten screenings.

### **Data Analysis Plan**

Specific aim one will be addressed through developmental activities to create and refine the intervention (see description of Deliverables above). This will include the creation of streaming videos, consumable materials, technical innovations to realize program components, and the manualized procedures. For the pilot, multiple baseline study, data will be analyzed by visual inspection to see whether slope and level of the measures change upon the initiation of the intervention and remain stable for the baseline phases (WWC, 2017). A key analysis will be an investigation of whether any changes in slope and level were dependent on phase change, and whether any such changes were replicated across cases. Across phases, the study investigators will consider the immediacy of effect, overlap, and consistency of data in similar phases (What Works Clearinghouse, 2019). We will collect teacher ratings of acceptability and observations of adherence.

Data analyses will also address specific aim two, "Investigate whether key academic and social outcomes are significantly improved in an intervention to prevent the RAE (immediately and after a delay) vs. KAU." For each of the outcome measures, data will be analyzed using analyses within SPSS. The analysis will be a 3 (Group: RAE Prevention Immediate, RAE Prevention Delay, KAU) by 4 (Time: Pre-treatment, Mid-year, End-of-year, First Grade Follow-up) Mixed Models analysis with group as the between group factor and time as the within subject factor. Also, using procedures outlined in Cohen (1992), effect sizes will be calculated to display the magnitude of treatment effect for the RAE programs relative to KAU (for dichotomous outcomes we will calculate odds ratios or relative risk). Effect sizes will be calculated for each outcome measure. Of particular interest are also variables related to establishing the mechanisms responsible for intervention effects and analysis of acceptability and implementation fidelity.

Most of the process measures collected in this study are descriptive and will help establish the feasibility of procedures for a larger R01 application. Thus, all descriptive information on adherence to study procedures and compliance with study assessments will be collected to evaluate the feasibility of this approach within a larger trial. Further, we will evaluate whether there are any negative side effects of the RAE prevention intervention, by inspecting whether teachers differentially rate children in the RAE groups as more symptomatic/impaired as the intervention is implemented (e.g., children may initially behave worse prior to getting better if the DRC is subjecting them to behavioral demands).

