### Pilot Study of RAE Prevention Timing and Effectiveness

To explore the relationship between the hypothesized mechanisms of treatment and key outcomes, a small randomized trial will be conducted to investigate the feasibility and promise of the proposed treatment for modifying the hypothesized treatment targets. It is currently unclear when the RAE prevention should be optimally implemented. On

the one hand, it may be beneficial to work with teachers immediately upon school entry, prior to the development of frequent relative comparisons that disadvantage the relatively young child in the class with ADHD. On the other hand, one might speculate that the intervention may be better positioned to promote teacher change after they have had frequent experiences with the child, and the relative comparisons have occurred, providing an active target for modification through intervention. Teacher acceptance and intervention feasibility may also vary based on implementation timing. Therefore, a pilot trial will be conducted that can compare the feasibility, effectiveness, and acceptability of these two competing intervention initiation timepoints, compared to a no intervention condition.

The sample of kindergarteners will be drawn from the school districts in Erie County. During the summer preceding each academic year, the UB researchers will partner with the school districts to attend kindergarten screening visits. All children who will enroll in kindergarten for the upcoming fall must come to the district office or designated school to enroll in the kindergarten year. We will partner with district administrators to provide time for study staff to introduce the study and request parental consent for participation. We will include all children born between 8/1 and 11/30 of the current school year. Specifically, children born in the

months of August, September, October, or November will be designated as relatively young for kindergarten.

The informed consent process will include a discussion of the risks/benefits of the planned study approach, and inform parents of their alternative choice (enroll in kindergarten as usual). Our enrollment plan is feasible given the overall level of kindergarten enrollment each year. We expect to enroll 30 participants per year.

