Inclusion criteria will include a child who is: (1) enrolling in kindergarten for the first time; (2) has a date of birth is between 8/1 and 11/30 of the current academic year; (3) does not have an Individualized Education program for behavioral concerns; and (4) has elevated symptom ratings of ADHD. Excluded will be any child outside of the targeted birthdate range, currently in restrictive special education placements for behavior (as this is a targeted study outcome), or taking psychoactive medication for mood, behavior, or inattention.

During kindergarten screening we will include children who have at least six symptoms endorsed at clinically significant levels via parent and/or preschool teacher ratings on the DBD rating scale across inattentive and/or hyperactive/impulsive presentations (Pelham, Gnagy, Greenslade, & Milich, 1992). Because we are exploring whether symptom ratings worsen during the school year, based on group assignment, we do not require a research-based, DSM diagnosis of ADHD, but expect our sample to illustrate symptom levels that place the child at risk for kindergarten classroom impairment due to ADHD. This approach also includes students who will eventually meet criteria for combined presentation, but exhibit primarily hyperactive/impulsive symptoms due to the lack of attentional demands in preschool/child care settings (Lahey, et al., 2005). Random assignment will be stratified by sex to distribute proportionally across groups. The project will purposely only include children born in the last quarter of the school year, as this is the key demographic of interest in the present proposal.

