Children whose parents provide permission will be enrolled in (1) kindergarten as usual; (2) the RAE prevention intervention implemented immediately (i.e., in October following the assessment); or (3) the RAE prevention intervention implemented at mid-year (i.e., in February). Given variability in birthdays, the large number of kindergarten classrooms currently in the are targeted, and the modest study demands for parents, we expect to meet all recruitment targets outlined in this application. Children assigned to the RAE prevention groups will have a school psychologist consultant assigned to the student for the duration of the school year. The consultant will work with the child's primary teacher to provide the preliminary training on the RAE and positive classroom management strategies, and to establish a DRC over the course of two consultation visits.

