*Kindergarten as Usual (KAU) group.* Consultants will conduct an initial meeting with each teacher of children in the KAU group to describe study procedures and establish regular classroom observation times. This condition is conceptualized as a kindergarten as usual control and serves as the counter-factual condition.

Consultants will be M.A. level school psychology specialists or special education teachers appointed to the project. We have chosen to use individuals with these credentials to increase the external validity of the

intervention as these individuals are likely to be called upon to consult with teachers regarding the behavior of children with ADHD as well as be involved in the assessment of children with ADHD in many school districts.

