### ***Outcome Measures.***

Outcome measures will be collected at the beginning of the kindergarten year in October, the middle of the kindergarten year in January, at the end of the kindergarten year in May, and at the beginning of the 1st grade year in October. These four assessment points will provide data on the proximal outcomes of the study manipulation and distal outcomes of the manipulation, and they will double as an assessment of the feasibility of the team's measurement plan and ability to retain participants in a longitudinal design (for both treatment and control groups).

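### The 3-by-4 mixed model does not adjust for the October score: its contrasts are valid if October ratings are unaffected by knowledge of the arm, but usually less precise than the same data allow

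*Combined protocol and SAP*

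**What the plan says.** The Data Analysis Plan applies one model to every outcome: three groups (immediate, delayed, KAU) by four times (pre-treatment, mid-year, end of year, first-grade follow-up), as a "Mixed Models analysis with group as the between group factor and time as the within subject factor". Group and time are the only terms named. No section adds a baseline covariate or a common baseline mean.

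The aim behind the model is to "Investigate whether key academic and social outcomes are significantly improved in an intervention to prevent the RAE". In addition, "effect sizes will be calculated to display the magnitude of treatment effect for the RAE programs relative to KAU". The plan does not say which contrast tests the treatment, or whether the effect sizes come from change scores, follow-up levels or adjusted differences.

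Three facts from the sections on the pilot study and on outcome measures bear on this:

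- Assignment is random: "Random assignment will be stratified by sex to distribute proportionally across groups".
- The October assessment comes before treatment. The intervention is "implemented immediately (i.e., in October following the assessment); or (3) the RAE prevention intervention implemented at mid-year (i.e., in February"), and "Outcome measures will be collected at the beginning of the kindergarten year in October, the middle of the kindergarten year in January", with further assessments in May and in October of first grade.
- On size, the only figure is "We expect to enroll 30 participants per year".

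**The concern.** In a randomised trial the arms have the same expected score before treatment. A model with a free October mean in each arm does not use that fact. With complete data its group-by-time contrasts are differences in change from October, so all the noise in the October score enters the comparison. Adjustment removes only the predictable part of that noise and generally gives a narrower interval from the same children.

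What is at stake is precision. The Statistical Power section puts feasibility first and declines to use the pilot to plan an efficacy study. Aim two nevertheless asks whether outcomes are significantly improved, and an effect size is promised for each one. With about 10 children per arm per year those intervals will be wide, so a nearly free reduction is worth having.

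**Working it through.** The documents give no power or precision figure, so there is nothing to reproduce.

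**Inputs.** From the documents: three arms, four assessments, 30 children per year. Assumed: equal split (n = 10 per arm), no missing data, SD = 1 at every time, one common correlation r, two-sided 5%.

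**Formulas** for one RAE arm against KAU at one later time:

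- Change from October: SE = √(4(1−r)/n), 3n−3 = 27 df, t = 2.052.
- Unadjusted level: SE = √(2/n) = 0.447, 27 df.
- Adjusted for October: SE = √(1−r²) × average of √(2/n + d²/W), where d is the chance October difference and W the within-arm sum of squares; 3n−4 = 26 df, t = 2.056. The average is 0.456 at n = 10, against √(2/n) = 0.447 with no small-sample penalty.

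Example at r = 0.5. Change: √(4 × 0.5/10) = 0.447, half-width 2.052 × 0.447 = 0.92. Adjusted: √0.75 × 0.456 = 0.395, half-width 2.056 × 0.395 = 0.81. The reduction is 12%.

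| r | Half-width, change | Level | Adjusted | Gain over change | Gain over the better of the two |
|---|---|---|---|---|---|
| 0.3 | 1.09 | 0.92 | 0.89 | 18% | 3% |
| 0.5 | 0.92 | 0.92 | 0.81 | 12% | 12% |
| 0.7 | 0.71 | 0.92 | 0.67 | 6% | 6% |
| 0.8 | 0.58 | 0.92 | 0.56 | 3% | 3% |
| 0.9 | 0.41 | 0.92 | 0.41 | 0.5% | 0.5% |

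Power for an assumed 0.8 SD effect, change against adjusted: 31% and 43%, 41% and 50%, 61% and 66%, 78% and 80%, 97% and 97%. Simulation with 20,000 trials per r agrees; rejection with no effect is 0.048 to 0.052 for both, so both analyses are valid.

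**Four-wave check.** The figures above are two-wave illustrations. Generalised least squares on the four-time model at n = 10, free against common October mean, gives SE 0.529 and 0.427, 0.447 and 0.387, 0.346 and 0.319, 0.283 and 0.268, 0.200 and 0.195 at the same five values of r. The pattern is the same.

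**Sensitivity.**

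- Twenty per arm, r = 0.5: half-width 0.63 (change) against 0.55 (adjusted).
- Unequal SDs. With k = later SD / October SD, the change variance per child in later-SD units is 1 + 1/k² − 2r/k, against 1 − r² adjusted (before the small-sample penalty). At k = 1.25 the gain over change is 10%, 4%, −1%, −2% and 0.5%. At k = 0.8 it is 28%, 23%, 19%, 18% and 20%.
- Correlation falling with time, r = 0.7^(months/3): 0.70 in January, 0.44 in May, 0.24 in first-grade October. The gain over change is 6%, 14% and 20%. Where r is below 0.5 the level contrast is the better comparator; against it the May gain is 1 − (2.056 × √(1−0.435²) × 0.456)/(2.052 × 0.447) = 8%, and the first-grade gain, by the same formula, is about 1%.

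**If October ratings are shifted by knowledge of the arm.** Let the shift be b. If it does not persist, the change contrast moves by −b and the adjusted contrast by about −r·b. Neither is clean.

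**The case against.** **The comparator is inferred.** The plan does not write out an interaction or a contrast. A free October mean in each arm is the standard reading of a 3-by-4 factorial, not a stated choice. This stands, and it limits the claim. A reader might quote an 18% gain (against change at r = 0.3) or 56% (against unadjusted level at r = 0.9). Each compares adjustment with the worse of two contrasts when the plan commits to neither. The fair comparison is the last column of the table.

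**The intervals are not those of the planned model.** This also stands: with all four waves and a pooled compound-symmetry covariance (81 df), the change half-width at r = 0.5 would be 0.89, not 0.92. The adjusted interval would narrow too, so the relative gain largely survives.

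**Validity depends on when assignment is disclosed.** Only the classroom observers are described as blind. Teachers complete the symptom, impairment and academic ratings, and parents also rate symptoms. No section dates disclosure, and the meeting at which "Consultants will conduct an initial meeting with each teacher of children in the KAU group to describe study procedures" has no date. A reader might infer that the October ratings are contaminated. The documents do not show this: October is labelled pre-treatment and the immediate arm starts after it. But the condition has to be stated, and reverting to the unconstrained model would not repair the problem if it occurred.

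**The consequence is small.** In a pilot that puts feasibility first, that is right, and it sets the weight of the point.

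**Conclusion.** The point holds as an optional efficiency improvement. Provided October scores are not influenced by knowledge of the arm, the planned group-by-time contrasts are valid but usually less precise than October-adjusted ones.

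With 10 per arm and equal SDs, the gain over the better unadjusted contrast is at most about 12%, near r = 0.5, and falls to 3% or less at r = 0.3 and at r of 0.8 or more. That ceiling depends on equal SDs: the gain can be larger if later scores vary less than October scores, and can become a loss of about 2% if they vary 1.25 times as much. N, allocation and r are all assumed. Confidence is high in the algebra and lower in the size of the benefit here.

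A reader might infer that the analysis is biased or that its tests are invalid without adjustment. Neither follows: under randomisation, and with October ratings unaffected by knowledge of the arm, both analyses are unbiased and keep their error rate.

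**What to change.** In the Data Analysis Plan:

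1. Fit October as a response with one common mean across the three arms, with group-by-time terms for January, May and first-grade October; or use the October score by time as a covariate.
2. Name the treatment contrasts as each RAE arm against KAU at assessments after that arm starts: January, May and first-grade October for the immediate arm; May and first-grade October for the delayed arm, whose January assessment precedes its February start.
3. Compute the effect sizes, with 95% confidence intervals, from these adjusted differences.
4. Complete the October ratings before assignment is disclosed to the rater, or record where this was not so. For such ratings report both the adjusted and the unconstrained results as a sensitivity analysis, and state that neither removes the bias.

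The cost is a few lines of analysis text and one degree of freedom, already counted in the half-widths above. No new data, visits or children are needed. The covariate form loses children with no October score (with one missing per arm of 10, about 1.09 times the variance of the common-mean form at r = 0.5), so it needs a stated rule for them.

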### **Statistical Power**

We are purposely not using this pilot study as a mechanism to generate effect size estimates for an efficacy study given the clear caution in the field against this as a goal for pilot studies such as this one (see Kraemer et al., 2006; Leon, Davis, & Kramer, 2011). Rather, the pilot study will be prioritized as a way to determine the promise of the procedures to be implemented reliably and with integrity in authentic school settings. Further, we will explore whether the hypothesized mechanisms are related to study outcomes as described above.

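### Randomisation is stratified by sex but the group-by-time model has no sex term; if sex is prognostic, visit-level comparisons between arms are modestly conservative

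*Combined protocol and SAP*

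**What the plan says.** The section on the Pilot Study of RAE Prevention Timing and Effectiveness names one restriction on the randomisation: "Random assignment will be stratified by sex to distribute proportionally across groups". No other stratification factor is named, and block sizes are not described. On numbers it says only "We expect to enroll 30 participants per year"; the number of enrolment years and the allocation ratio are not given.

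The Data Analysis Plan applies a 3 (group) by 4 (time) model to each outcome measure, a "Mixed Models analysis with group as the between group factor and time as the within subject factor". The four times include the pre-treatment assessment. The sentence is complete, and neither sex nor any other covariate appears in it or elsewhere in the plan. The plan adds that "effect sizes will be calculated to display the magnitude of treatment effect for the RAE programs relative to KAU", but does not say which contrast from the model is the main one: the group effect, the difference at one visit, or the group-by-time interaction.

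The Statistical Power section gives no target effect, alpha or power.

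**The concern.** Stratifying by sex is meant to give the arms the same mix of boys and girls. Once that is achieved, a boy-girl difference in an outcome cannot contribute to the difference between arms, so the true sampling variance of that difference depends only on variation within each sex. A model that omits sex estimates its residual variance from all children within an arm, boys and girls together, and so includes the sex difference. Its standard error is then larger than the true one, its interval wider than the design earns, and its test conservative. The design restricts the allocation and the analysis ignores the restriction.

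At stake is some precision in a small trial. Bias and false positives are not at issue, because the error runs in the cautious direction. The plan does ask whether outcomes are significantly improved, and also looks for children in the intervention arms being rated worse, so calibrated tests are of some use here.

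**Working it through.** The plan has no power or precision figure to reproduce, so the check starts from the model.

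**Inputs from the documents:** three arms, four visits, sex as the only stratification factor, a model with group and time only, 30 children enrolled per year.

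**Assumptions, not in the documents:** 1:1:1 allocation; 20 per arm, 60 in all (two cohorts of 30), with 10 and 30 per arm as the range; proportion of boys p = 0.7; exact sex balance across arms; boy-girl gap d of 0.3, 0.5 or 0.8 within-sex SDs; between-visit correlation 0.6; two-sided 5% tests.

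**Arm difference at one visit.** Set the within-sex variance to 1. Omitting sex adds p(1 − p)d² to the residual variance, while the true variance of the arm difference is unchanged. With N children in all and three fitted means, the standard error is too large by the factor

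√[1 + (N/(N − 3)) · p(1 − p)d²].

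Here p(1 − p) = 0.7 × 0.3 = 0.21 and N/(N − 3) = 60/57 = 1.053.

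- d = 0.3: √(1 + 1.053 × 0.0189) = 1.010, an excess of 1%.
- d = 0.5: √(1 + 1.053 × 0.0525) = 1.027, an excess of about 3%.
- d = 0.8: √(1 + 1.053 × 0.1344) = 1.068, an excess of about 7%.

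Sample size hardly matters. At d = 0.8 the factor is 1.072 with 10 per arm and 1.067 with 30. With half boys and half girls, and without the N/(N − 3) factor, it is 1.005, 1.031 and 1.077 for gaps of 0.2, 0.5 and 0.8 SD.

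**Effect on the tests.** The 5% critical value on 57 degrees of freedom is 2.00. Multiplied by the three factors it acts like 2.02, 2.06 and 2.14, with two-sided tails of about 4.8%, 4.4% and 3.7%. Simulation with 40,000 replicates and balanced arms gave about 4.8%, 4.5% and 3.8%, and about 5% once sex was in the model. For a true arm difference of 0.8 SD at one visit, simulated power was about 65% without sex and 70% with it when the gap is 0.8 SD. With no sex effect it was 70% either way.

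**Change from October.** A constant gap is in both measurements of every child and drops out of the change, so the factor is 1.00 with or without sex. If the gap widens by 0.5 SD, the within-sex variance of change is 2(1 − 0.6) = 0.8, and the factor is √(1 + 1.053 × 0.21 × 0.25/0.8) = 1.034, an excess of about 3%.

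**If sex is not balanced.** With simple, unblocked allocation within each sex, the model without sex is not miscalibrated: the sex difference then really is part of the sampling error. A simulation of 6,000 replicates at 20 per arm on average (70% boys, gap 0.8 SD) gave an average standard error of 0.343 without sex and 0.325 with it, with reported and true error agreeing to within about 2%. Adding sex still gains precision in that case.

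**The case against.** The strongest objection is that a 3 by 4 model with a pre-treatment level would normally be read through group-by-time, that is, change from October. There a constant sex gap cancels and nothing is lost. This stands, and it limits the point to single-visit comparisons and to gaps that change over the year. It does not remove the point, because the plan does not name its contrast.

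Second, the size rests on assumptions. The documents give no sex effect for any outcome, and children enter only with at least six clinically significant ADHD symptoms, so both sexes are selected on something close to several outcomes. A gap of 0.8 SD in this sample has no support in the documents; at 0.3 to 0.5 SD the excess is 1% to 3%. Balance is intended but, without a described blocking method, not assured. All of this stands.

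Third, this is a pilot directed at feasibility. The Statistical Power section says "We are purposely not using this pilot study as a mechanism to generate effect size estimates for an efficacy study". That bears on how much the loss matters. It does not withdraw the planned tests or the effect sizes to be calculated for each outcome.

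Three stronger readings are tempting, and the documents do not support them:

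- A reader might infer that the standard errors are wrong as a matter of course. They are too large only if sex is prognostic and the scheme balances it.
- A reader might quote the group main effect, where the same assumptions (four-visit mean, variance (1 + 3 × 0.6)/4 = 0.7) give √(1 + 0.0525/0.7) = 1.04 and √(1 + 0.1344/0.7) = 1.09 for gaps of 0.5 and 0.8 SD. That contrast averages in visits before treatment: October for both intervention arms, and January too for the arm starting in February. It is a poor measure of the treatment effect.
- A reader might want cohort year added in the same way. Sex is the only stratification factor named, and the documents give no basis for the size of a cohort effect.

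**Conclusion.** The mismatch is real: the analysis omits the one factor by which children are randomised. Its consequence is conditional and modest. Under the assumptions of 70% boys, 20 per arm and balanced arms, standard errors for a difference at a visit are too large by about 1% to 7% over gaps of 0.3 to 0.8 SD, and actual test levels lie between about 4.8% and 3.7%. Contrasts of change lose nothing if the gap is constant and about 3% if it widens by 0.5 SD. Estimates are unbiased throughout. Including sex costs almost nothing if it turns out not to matter, so this is a free improvement of minor size. It is not a flaw that threatens the trial's conclusions.

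**What to change.** In the Data Analysis Plan, add sex and sex-by-time as fixed effects to the group-by-time model for each continuous outcome, and state that arm differences will be reported averaged over the sexes. The sex-by-time term lets the gap differ between visits, which is the only way sex affects the change contrasts. In the same paragraph, name the contrast of main interest. In the paragraph on random assignment, say whether allocation within each sex is blocked, without giving block sizes.

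The cost is one or two sentences and 1 + 3 degrees of freedom. With 60 children the between-child residual falls from 57 to 56 and the within-child residual from 57 × 3 = 171 to 168. With 30 children the falls are from 27 to 26 and from 81 to 78. No new data are needed, since sex must be known in order to randomise. The change is best made before any outcome data are analysed by arm.
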